1.1 Title

Promoting mental health and wellbeing through a school-based intervention – a study using a mixed-methods, quasi-experimental Extended Selection Cohorts design – the 5Ways@School study. Norwegian short title: Prosjekt fem gode vaner (Hverdagsglede Skole).

1.2 Funding

Sponsored by Moss Municipality, Norway. Funded by Moss Municipality, Norwegian Institute of Public Health, PROMENTA research centre, University of Oslo, the County Governor of Oslo og Viken, and the Norwegian Research Council (project no. 345560). The County Governor and the Research Council have no role in the research process.

2.1 Background and rationale

Mental health problems are common among children and adolescents worldwide, with prevalence estimates of 10-20 % (Kieling et al., 2011). In recent years, the prevalence of mental distress and common mental disorders like depression and anxiety has increased in adolescents, especially

among girls (Mojtabai et al., 2016; von Soest et al., 2022). Similarly, loneliness has increased recently among young people (Lee et al., 2020). The COVID-19 pandemic has been challenging for the mental health and wellbeing for many children and adolescents; and in Norway higher levels of depressive symptoms and less optimistic future life expectations have been observed among adolescents during the pandemic (von Soest et al., 2022).

The global challenge of mental health problems calls for different approaches; both treating mental health disorders, preventing mental health problems, and promoting mental health and wellbeing for all. School-based interventions are a primary tool in universal prevention to promote mental health and alleviate loneliness. Thus, the World Health Organization has advocated for teaching of life skills in schools, i.e., teaching of abilities that are often taken for granted, but nonetheless are positively associated with mental health and wellbeing (World Health Organization. Division of Mental, 1994). Some school-based interventions have had positive short-term effects in teaching life-skills (Kavanagh et al., 2009), building social and emotional competence (Taylor et al., 2017), reducing mental distress and/or preventing common mental disorders (Werner-Seidler et al., 2017), while other interventions have failed in finding such effects (Sælid et al., 2022). To sum up, well-designed interventions with a proven long-term effect on mental health and/or loneliness are rare.

The Norwegian government decided to implement “public health and life skills” as a new interdisciplinary topic at all primary and secondary school levels from the year 2020, in order to promote mental and somatic health. Several teaching programmes aimed at promoting mental health and life skills are available in Norway, but few have well-documented effects. Hence, there is a need for teaching materials that have proven health promoting effects.

The purpose of the current study is to develop an evidence-based, health-promoting intervention and investigate its effects on well-being and mental health among school pupils aged 10 to 16 in Moss municipality, Norway.

In the first phase of the study, we will pilot the intervention at two selected schools in Råde municipality. In the second phase of the study, we will run a full-scale trial at the public schools in Moss (16 schools; approximately 3,300 pupils). For the latter purpose, we will use the quasi-experimental Extended Selection Cohorts design. We will investigate the changes in the pupils' scores on health behaviours, mental health, and well-being from baseline to different timepoints of data collection during a 12 months follow-up period.

2.2 Objectives

Our objectives are:

1. To adapt the existing *Five ways to wellbeing* course for adults to a school setting, and to pilot the intervention in two schools.
2. To explore how participating pupils, teachers, and other school personnel experience the pilot intervention, and identify aspects that should be adjusted before proceeding to a full scale trial.
3. To examine how the teachers deliver the intervention in the full scale trial; their motivation, obstacles they encounter, general satisfaction with the intervention, and their adherence to the intervention manual (i.e., fidelity).
4. To investigate whether the intervention is acceptable and experienced as useful for participating school pupils, parents, teachers, and other school personnel.
5. To investigate whether the intervention have any adverse effects, such as triggering negative emotions.
6. To evaluate the process of implementation.
7. To describe the pupils' wellbeing and mental health at baseline (November 2023).

8. To examine the immediate and long-term effects of the intervention on the pupils' wellbeing and mental health.
9. To assess for whom the intervention is effective (i.e., subgroup analysis and moderation analysis, for example SES, gender, baseline symptom levels, etc.).
10. To investigate what mechanisms explain potential improvements in wellbeing after exposure to the interventions.

2.3 Trial design

In phase 1, we will conduct a pilot study in two chosen schools in Råde Municipality.

In phase 2, we will use the quasi-experimental Extended Selection Cohorts (ESC) design. The ESC design is an option for real-life settings when an RCT is not feasible, because the ESC design makes it possible to compare same-age treatment groups. For the current study, a cluster-RCT of sufficient power would have needed a large number of schools and is therefore not feasible. The ESC design is a cohort-longitudinal design with adjacent cohorts, that are measured at two or more time points; a design that has been used to evaluate effects of school-based interventions, for example anti-bullying programmes (Kärnä et al., 2011; Olweus, 2005) and a programme that promotes physical activity and a healthy diet (Takens et al., 2020). Each cohort comprises subjects of approximately the same age. In a standard RCT design, the pupils, classes, or schools are randomly allocated to different intervention and control groups; but in the ESC design intervention and control groups belong to the same schools, and fewer schools or pupils are therefore needed. The cohorts that are exposed to the intervention are compared with unexposed cohorts from the same school, ensuring that the research subjects are recruited from a relatively stable population with the same socio-demographic characteristics (Olweus, 2005; Takens et al., 2020). This is important when studying health and health behaviour, which differs according to different SES and ethnicity groups. The ESC design does not, however, allow us to control for general societal time trends that coincide with the intervention.

In our study, we will collect data from each cohort (i.e., school grade) five times, starting in November, 2023 (baseline), followed by January, February, March, and November, 2024.

At 12 months follow-up, each cohort will be compared to the same-age adjacent baseline cohort group (see Figure 1). For instance, the measures of the grade 5 cohorts that will have been *exposed* to the intervention (grade 5 in 2024–2025) will be compared to the baseline measures of the *unexposed* grade 5 cohorts (grade 5 in 2023–2024).

Figure 1. How exposed cohorts can be compared to unexposed cohorts at 12 months follow-up

	Cohort A	Cohort B	Cohort C	Cohort D	Cohort E	Cohort F
Baseline (Nov. 2023)	Grade 5	Grade 6	Grade 7	Grade 8	Grade 9	Grade 10
Intervention						
Follow-up (Nov. 2024)	Grade 6	Grade 7	Grade 8	Grade 9	Grade 10	

In order to separate any effects of the intervention from changes in variables due to other causes, we will apply a «wait list control group» element, i.e., delayed intervention: approximately $\frac{1}{2}$ of the schools will start the intervention in November 2023, while the remaining schools will start the intervention approx. 14 weeks later. We will collect data from all pupils in November 2023, and in February 2024 we will compare the scores of the intervention group with the «wait list» group.

3 Methods

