3.6 Participant timeline

The time schedule of enrolment, interventions and assessments for participants is shown in Figure 2.

Figure 2. Schedule of enrolment, intervention, and assessments.

TIMEPOINT	Enrolment	Allocation	Post-allocation				
	Nov. 2023	Nov. 2023	Nov. 2023	Jan. 2024	Feb. 2024	Mar. 2024	Nov. 2024
ENROLMENT:							
Informed consent	X						
Allocation		X					
INTERVENTION – FIRST GROUP				→			
INTERVENTION – SECOND GROUP:					→		
ASSESSMENTS:							
Questionnaires on health & wellbeing			X	X	X	X	X
Socio-demographics			x			X	
Feasibility & fidelity				X (1st group)	X (2nd group)		

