3.7 Sample size

During the study period, there will be approximately 3,300 pupils in grade 5 to 10 in the public schools in Moss, who will be invited to participate. We have a conservative estimate of 70 % participation, i.e., about 2,300 participants. All pupils in 157 school classes in Moss municipality will be invited to participate in our study. The average number of pupils in a school class in Moss is 21, and we assume that 15 pupils per class (i.e., 70 %) participate.

Estimating statistical power in a clustered trial that is not randomized can be challenging, as we need to account for the correlation within clusters and the variation between clusters, as well as the variation in the outcome measure(s). Our approach to determine statistical power was to run a power analysis available at <http://psychstat.org/crt2arm> with the following assumptions:

- Sample size (i.e., number of participating pupils per class): 15
- Effect size: 0.16
- Number of clusters (i.e., number of school classes); 157
- Intra-class correlation: 0.05

- Significance level: 0.05
- Power curve: No power curve
- H1: Two-sided test

This analysis resulted in a power of 0.8411. The assumption that our intervention might have an effect size of 0.16 is based on previous studies, see (Tanner-Smith et al., 2018; Taylor et al., 2017; Werner-Seidler et al., 2017).

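### The one concurrently controlled contrast the plan names, early versus delayed schools in February 2024, has no stated rule for assigning the 16 schools; start order could be drawn at random within school stage at no cost in schools or pupils

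*Combined protocol and SAP*

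**What the plan says.** Section 2.3 adds a wait-list element to the cohort design. Its purpose is stated: "In order to separate any effects of the intervention from changes in variables due to other causes". About half of the schools begin in November 2023, and "the remaining schools will start the intervention approx. 14 weeks later". All pupils are measured in November 2023, and "in February 2024 we will compare the scores of the intervention group" with those of the wait-list group.

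The same section concedes the limit of the 12-month cohort comparison: "The ESC design does not, however, allow us to control for general societal time trends that coincide with the intervention". It gives one reason for not randomising: "a cluster-RCT of sufficient power would have needed a large number of schools and is therefore not feasible".

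Figure 2 in section 3.6 shows an Allocation step in November 2023 without a method. Section 3.7 opens its power discussion with "Estimating statistical power in a clustered trial that is not randomized can be challenging". Section 3.8 says that all pupils in grades 5 to 10 are exposed to the programme.

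The plan already holds several useful parts:
- Grade is recorded for every pupil (3.4.7).
- The multilevel model covers five waves, with class and school levels and subgroup analyses by grade and by baseline scores (3.11).
- The school that runs another programme is to be taken into account (3.3, 3.4.8).

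Section 3.11 does not name a start-group or start-group-by-wave term, or a stage or grade adjustment for the February comparison. Section 4.5 removes school name and class membership from the final dataset.

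**The concern.** The plan's protection against time trends rests on which schools start first. If schools were placed by readiness, leadership interest or timetable, the two groups could change differently between November and February for reasons unrelated to the programme.

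Repeated measures on the same pupils largely cancel stable level differences between the groups. They do not cancel differences in change. Grade mix can be adjusted for because grade is recorded, but precision is lost if stage is unbalanced. Unmeasured school factors cannot be adjusted for, and only a random draw guards against systematic selection on them. Without a stated rule, a reader can judge neither risk.

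**Working it through.** **1. Is February the only concurrent contrast?** It is the only one the plan names. The 12-month comparison sets November 2024 scores against another cohort's November 2023 baseline, so its controls are a year older. Fourteen weeks is 98 days, so a first start no earlier than 1 November puts the delayed start at about 7 February or later. The January 2024 wave therefore also precedes it and could give a second concurrent contrast. That contrast would use the same split of schools and share the same gap.

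**2. The plan's own power figure.** Inputs from section 3.7: J = 157 classes, n = 15 pupils, effect f = 0.16, ICC = 0.05, two-sided 0.05.
- λ = √[J f² / (4(ICC + (1 − ICC)/n))] = √[157 × 0.0256 / (4 × 0.1133)] = 2.978.
- The noncentral t with 155 df gives power 0.8411, which matches the plan.

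**3. The same effect with schools as the allocated units.** Section 2.3 assigns start time by school. There are 16 schools, 157/16 = 9.81 classes per school and 9.81 × 15 = 147.2 pupils per school. The documents give no school-level ICC, so I split the total of 0.05 into an assumed school part ρs and a class part 0.05 − ρs. One df is used for stage, leaving 13.
- Variance of a school mean: v = ρs + (0.05 − ρs)/9.81 + 0.95/147.2.
- λ = √[16 × 0.0256 / (4v)].

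| Assumed ρs | Power, no baseline adjustment | Power if baseline removes half the variance (assumed) |
|---|---|---|
| 0 | 0.79 | 0.97 |
| 0.005 | 0.65 | 0.91 |
| 0.01 | 0.54 | 0.83 |
| 0.02 | 0.41 | 0.68 |
| 0.05 | 0.24 | 0.42 |

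To first order these figures are the same whether start order is drawn or chosen. The power argument in section 2.3 therefore does not bear on how start order is set.

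**4. Stage imbalance, worst-case illustration.** The documents do not give the number of schools per stage. Assume 8 v 8 schools, separate primary and lower-secondary schools, 1,650 of the 3,300 pupils in each stage, equal school size within stage, and k = 2 to 6 lower-secondary schools. Put all k in one start group.
- Gap in the grade 8–10 share = 1/(1 + (8 − k)/(16 − k)) = 0.70, 0.72, 0.75, 0.79, 0.83. With the most even split it is 0, 0.21, 0, 0.15, 0. If all 16 schools covered both stages it would be 0.
- Squared correlation of start group and stage = k/(16 − k). Standard-error multiplier after stage adjustment = √[(16 − k)/(16 − 2k)] = 1.080, 1.140, 1.225, 1.354, 1.581. With the most even split it is at most 1.013.
- In this extreme one group has no lower-secondary schools, so the adjusted estimate rests on primary schools alone (8 − k against 8). It carries over to grades 8–10 only if the effect is constant, whereas section 3.11 expects larger effects in younger pupils.

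**5. What stratifying does.** With an assumed 10 primary and 6 lower-secondary schools, an unstratified 8:8 draw puts five or six of the six in one group with probability 2 × (0.056 + 0.003) ≈ 0.12. A stratified draw rules this out and still leaves C(10,5) × C(6,3) = 252 × 20 = 5,040 allocations.

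**6. The school-level change term.** If 1% of the change-score variance lies between schools (assumed) and the model omits it, then with 2,300/16 ≈ 144 pupils per school the design effect is 1 + 143 × 0.01 = 2.43. The standard error would be about 1 − 1/√2.43 = 36% too small.

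**The case against.** The design is openly quasi-experimental, so the absence of randomisation is neither a contradiction nor concealed. The actual start order may have been random or balanced and simply not described; the remark in section 3.7 describes the trial as a whole. The model already has repeated measures, a school level and recorded grade, which deal with much of the stable difference between groups. With 16 schools, even a draw leaves chance imbalance.

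All of this stands, and it limits the point in three ways.
- A reader might infer that schools were selected in a way that biased the comparison. The documents do not show this; they show only that no rule is stated.
- A reader might take the 70 to 83 point gap and the 8% to 58% loss of precision as the size of the problem in this trial. They come from an assumed school structure and the worst possible split, which nothing in the text suggests. They support balancing by stage; the benefit of randomising as such is not quantified.
- A reader might infer that a random draw makes February an adequately powered test. Step 3 shows that it does not change power.

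What the objection does not answer is why start order should be left unstated or chosen, when the only reason given against randomising concerns the number of schools.

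**Conclusion.** The point holds as a design improvement and a reporting gap. The plan relies on the February comparison to isolate the programme effect, gives no assignment rule in the text available for review, and offers no reason that applies to start order.

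The direction and size of any bias cannot be derived from the documents. Power for the school-assigned contrast, about 0.24 to 0.79 without baseline adjustment, depends on an assumed school-level ICC; the plan's 0.8411 treats 157 classes as the allocated units.

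To call February the only contrast with concurrent controls would go too far, because January 2024 could supply another. So would the view that stage adjustment costs only precision: in the extreme split it also narrows the estimate to primary schools. The point should be acted on; confidence is medium, because the method actually used is unknown.

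**What to change.** - Draw the start order of the 16 schools at random, stratified by school stage, and describe the draw at the Allocation step.
- Pre-specify one February 2024 estimate with school as the allocated unit. Either (a) regress the February score on start group, November 2023 score and stage or grade, with a school random effect; or (b) use the planned repeated-measures model with start-group-by-wave and stage-by-wave terms plus a school-by-wave (random change) term, taking the February start-group-by-wave coefficient. In both, use small-sample degrees of freedom based on 16 schools.
- Keep coded school and class numbers and start group in the analysis file. Section 3.11 models school and class, while section 4.5 removes both from the final dataset.
- If the order is already fixed, state how it was chosen, use the same model, and interpret the contrast as non-randomised.
- Omitting the school with the other programme is at most an optional sensitivity analysis, since sections 3.3 and 3.4.8 already plan to account for it.

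The cost is a draw, a paragraph of text, coded identifiers and some loss of scheduling flexibility for the municipality. Stage as a two-level stratifier uses one degree of freedom: the two-sided 5% critical value moves from 2.145 (14 df) to 2.160 (13 df), a ratio of 1.007. No extra schools or pupils are needed.

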3.3 Intervention

Our intervention, *5Ways@School*, will be based on the *Five Ways to Wellbeing* programme, which is a set of evidence-based public mental health messages aimed at improving the mental health and wellbeing of the whole population. The *Five Ways* promote five dimensions of activities, each of them being associated with mental health and quality of life; making up a «mental health literacy tool box» (Aked et al., 2008). They were developed by the New Economics Foundation in the UK, and the *Five Ways to Wellbeing* programme is currently being used for adults in Norwegian Healthy Lifestyle Centres. Several studies have been conducted, examining potential benefits of the *Five Ways* and similar interventions (Mackay et al., 2019), and two studies are currently being conducted in Norway among adult populations (Eilertsen, 2020; Prydz, 2021). To our knowledge, there is no previous research on the *Five Ways* in Norwegian children or adolescents.

The *5Ways@School* intervention will be a teaching material consisting of five elements; Take notice, Be active, Keep Learning, Connect, and Give. The intervention will be given in an ordinary classroom setting by the class's main teacher in two school hours of 45 minutes each week for six consecutive weeks, i.e., a total of 12 school hours. The teaching sessions will consist of presentations of the five elements, videos, reflection exercises, focused group discussions, creative group work, and giving the pupils small "challenges" to practice what they have learned between the weekly sessions.

Prior to the intervention, the teachers will attend a whole day seminar where they will learn the scientific background of the intervention, the intervention manual will be presented, and any questions responded to. They will receive a copy of the intervention manual one week before this seminar. School nurses, social teachers, and other school personnel will also be given this seminar, so that they may use the same five elements in their follow-up of individual pupils who need extra support.

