3.4.9 Data on feasibility and acceptability

The teachers who will be teaching the interventions will be asked: "Based on your experiences, which of the five elements in the 5Ways@School do you think was 1) most useful for the pupils?, easiest for you to teach, and 3) most challenging for you to teach? The teachers will respond to these questions by choosing any of the five elements of the 5Ways@School: Take notice, Be active, Keep Learning, Connect, and Give.

The teachers will respond on a four-point scale from "agree completely" to "disagree completely" to the following items: 1) I was well motivated to teach the 5Ways@School, 2) I enjoyed teaching the 5Ways@School, 3) Teaching life skills through the 5Ways@School is a natural part of my job as a teacher, 4) I got sufficient information and/or training before I started teaching the 5Ways@School, 5) I think the pupils learned something new and useful, 6) There was too little activities in the 5Ways@School, 7) There was too much activities in the 5Ways@School, 8) I followed the teaching manual to a high degree, 9) I completed all the six lessons in the 5Ways@School, 10) I had to abbreviate one or more lesson(s), 11) I think that the 5Ways@School should be part of the ordinary school curriculum in 5h to 7th grade, and 12) I think that the 5Ways@School should be part of the ordinary school curriculum in 8th to 10th grade.

We will also investigate the experiences of school nurses, school leaders, and parents through focus group interviews.

Participating pupils will be given a questionnaire with the following items: 1) I enjoyed learning about 5Ways@School, 2) I learned something new, that I can make use of, 3) The teaching was easy to understand, 4) The teaching was boring, 5) The teaching was interesting, 6) There was too little activities, 7) There was too much activities, 8) The teaching made me sad, afraid, or angry, 9) The teaching made me happy, 10) I will practise more of the five ways in the future, 11) I think all pupils should learn about the five ways. The pupils will respond on a four-point scale from "agree completely" to "disagree completely".

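### For the second start group, Figure 2's February 2024 feasibility form comes before the last lesson and the March 2024 survey may too, with no further wave until November 2024

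*Combined protocol and SAP*

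**What the plan says.** Section 2.3 describes a staggered start. About half "of the schools will start the intervention in November 2023", while "the remaining schools will start the intervention approx. 14 weeks later". The scores of the two groups are compared in February 2024, with the later group as the wait-list control.

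The course in section 3.3 takes "two school hours of 45 minutes each week for six consecutive weeks, i.e., a total of 12 school hours".

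Section 2.3 sets five survey waves for every cohort, "starting in November, 2023 (baseline), followed by January, February, March, and November, 2024". Only months are given, and nothing is scheduled between March and November 2024.

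Figure 2 in section 3.6, as read from the PDF, has the feasibility and fidelity form under January 2024 for the first group and under February 2024 for the second.

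The teacher items in section 3.4.9 include "I completed all the six lessons in the 5Ways@School" and one on adherence to the manual. The pupil items include one on whether the teaching caused sadness, fear or anger. The text dates none of these forms.

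The objectives served are 3 (delivery and fidelity), 4 (acceptability), 5 (adverse effects) and 8, "To examine the immediate and long-term effects of the intervention on the pupils' wellbeing and mental health".

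**The concern.** The start dates, course length, survey months and form dates do not fit together for the second group. A form asking whether all lessons were completed is valid only after the last lesson. In February 2024 the second group can be at most about halfway through the course, and in that month it is also meant to be the untaught comparison.

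The March wave is the only other spring survey that could serve as this group's post-course measure. If it falls during the course, the group has no measure soon after completion. Section 3.11 nests the five measurements within pupils, classes and schools but does not define exposure at each wave. Nothing in the plan therefore prevents a mid-course March score from being analysed as post-programme, which would pull the estimated effect towards zero.

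**Working it through.** The plan states no finishing date for the second group, so there is no figure on this point to reproduce. Its one computed figure, the power in section 3.7, plays no part here.

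**Inputs**
- First start, S: 1 to 30 November 2023 (section 2.3 gives only the month).
- Delay: about 14 weeks, 98 days (section 2.3).
- Course: six consecutive weeks (section 3.3). The last lesson falls from day 35 (first day of week six) to day 42 (six full weeks) after the start.
- School breaks: the plan mentions none, so none are counted.

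**Step 1: second-group start = S + 98 days.**
- S = 1 November gives 7 February 2024.
- S = 30 November gives 7 March 2024.

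**Step 2: second-group finish = S + 98 + 35 to S + 98 + 42 days.**
- S = 1 November gives 13 to 20 March.
- S = 30 November gives 11 to 18 April.
- The overall range is 13 March to 18 April 2024.

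**Step 3: a form in February 2024.** Take the most favourable case, the earliest start and the last day of the month. From 7 to 29 February is 22 days, and 22/7 = 3.1 weeks of a six-week course. If the first group starts after 23 November, S + 98 days falls after 29 February and the second group has not begun. No November start with a delay of 13 to 16 weeks finishes by 29 February. At 12 weeks this happens only for S = 1 or 2 November with the last lesson on the first day of week six.

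The first group does not have this problem. S + 42 days runs from 13 December 2023 to 11 January 2024, so a January form can follow its last lesson.

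**Step 4: a survey in March 2024.** The latest day is 31 March. It follows completion only if S is no later than 31 March minus (delay + 35 or 42 days).

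| Delay | Second group finishes | Latest S for 31 March to follow completion (six full weeks / first day of week six) |
|---|---|---|
| 13 weeks | 6 March to 11 April | 19 / 26 November |
| 14 weeks | 13 March to 18 April | 12 / 19 November |
| 15 weeks | 20 March to 25 April | 5 / 12 November |
| 16 weeks | 27 March to 2 May | none / 5 November |

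At 14 weeks the greatest possible margin is 31 − 13 = 18 days. A survey before 13 March cannot follow completion for any S.

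**Step 5: early starts narrow the February window.** For S = 1, 12 and 19 November the second group begins on 7, 18 and 25 February. The February survey must come before those dates if the group is to be an untaught control, while the March survey must be held near the end of its month. Both can be met, but the plan does not fix either day.

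**Step 6: the gap if March misses.** At 14 weeks, a class finishing between 1 and 18 April waits until November 2024. From 18 April to 1 November is 197 days (28 weeks); from 1 April to 30 November is 243 days (35 weeks).

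**The case against.** The strongest reply is that the documents leave the timing open. They give months rather than days, and the delay is approximate. A late-March survey can follow the last lesson for first starts in roughly the first half of November. A reader might infer that the second group certainly has no post-course survey until November 2024; the documents do not establish that.

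A reader might also infer that the immediate effect is lost for about half the schools. It is not. Section 2.3 estimates the short-term effect from the February contrast, where the second group is the control, and objective 8 does not ask for a separate immediate effect in each start group.

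Nor are the process objectives lost. The first group's forms are unaffected, the focus groups have no fixed date, and answers covering part of a course are still data.

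The form's February column comes from a table read from PDF. In that table the first group's arrow sits under January although its teaching starts in November, so column positions need checking against the original figure. The text also does not say that the pupil reaction questionnaire belongs to the feasibility and fidelity row.

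Finally, section 3.11 is silent on exposure coding, so dilution is a risk and not a stated feature of the model.

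All of this stands and limits the point. It does not remove the conflict. If the form really sits in February, it precedes the last lesson under every November start at 13 to 16 weeks. If it sits in March, the cut-offs in Step 4 apply to it as well. Any school break would push completion later.

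**Conclusion.** The point holds as a scheduling conflict that must be reconciled between section 2.3, section 3.3 and Figure 2. At a 14-week delay the second group finishes between 13 March and 18 April 2024. A February form is at best 3.1 weeks into the course. A 31 March survey follows completion only for first starts up to 12 to 19 November.

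About half the schools are affected. If they hold half the planned participants, that is 2,300/2 = 1,150 pupils, although the plan does not give the split by pupils.

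At risk are the second group's own immediate change, the validity of its fidelity, acceptability and reaction answers (objectives 3 to 5), and the size of the estimate if mid-course March scores are treated as post-programme. The last cannot be quantified, because the plan does not define the exposure variable. The overall immediate effect remains estimable from the February contrast.

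The conclusion assumes November first starts, a delay of about 14 weeks, no school breaks, and that the February column in Figure 2 was read correctly.

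**What to change.** - **Forms.** Tie the teacher and pupil feasibility, fidelity and reaction forms to completion of the sixth weekly lesson in each class, not to a calendar month.
- **Spring wave.** Hold the existing March wave in all schools just after the second group's sixth teaching week, and state the survey days in section 2.3.
- **Figure 2.** Correct it to match, with calendar dates for teaching, surveys and forms in each group.
- **Model.** In section 3.11, code each measurement as before, during or after the programme from actual class dates.

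No wave, pupils or staff are added, and the February contrast is untouched. The cost is that the March snapshot moves a few weeks later, including the first group's March follow-up and the socio-demographic item that Figure 2 shows in that month.

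If the dates can no longer move, add the exposure coding alone, and do not report second-group March scores taken during the course as post-programme.
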